#### 4.4 Minorities and Women

Women and minorities will be enrolled in proportion to their representation in the population base from which this study was developed, specifically patients presenting to Intermountain hospitals located in Utah's Salt Lake, Washington, and Weber Counties. In order to provide generalizable data for the ED patient diagnosis groups studied in each Aim, there will be no specific selection criteria that differ between sex/gender and racial/ethnic groups. Hospitals in this study serve counties with a combined population of over 1.5 million individuals, including over 26% who are Hispanic or non-white race. We expect the sex, ethnic and racial mix of the enrolled patients to reflect the population served.

#### 4.5 Vulnerable Subjects

We anticipate that potentially vulnerable subjects are eligible for the study. Potentially vulnerable patient subjects include pregnant women, prisoners, and/or individuals with decisional impairment. The purpose of this project is to identify a cohort that reflects the diversity of the U.S. sepsis population. Therefore, we believe these individuals should not be excluded from the study since the study is of no more than minimal risk.

- 1. Data on vulnerable population membership will not be explicitly collected, and in fact attempting to identify and exclude members of potentially vulnerable populations could increase risk to both vulnerable patients and the overall subject cohort.
- 2. Altered mental status is also a common manifestation or complication of sepsis. Excluding patients with decisional impairment would therefore severely bias results of the planned analyses.
- 3. In implementation studies such as this, it is generally not possible to exclude vulnerable subjects. Aim III's intervention involves testing a new option for standard care for ED sepsis management, so excluding vulnerable populations could actually subject these patients to harm because exclusion would prevent their receiving standard care. Assessment for vulnerability status, moreover, would largely preclude the planned intervention by preventing activation of prehospital or ED triage alerts.

## 5. STUDY PROCEDURES

This study will measure the effect of a redesign of standard care for ED sepsis patients, specifically implementation of Code Sepsis protocol at Intermountain Medical Center. The study will include three phases with two groups during each phase. The primary analysis will only use data from phases #1 and #3 (see Figure 1 and 2).

Phase #0: Protocol development (1 year, overlaps with phase #1)

- Control EDs: N/A
- Intervention ED: A small number of suspected sepsis patients (<10) may undergo anonymous observation to understand care processes involved in ED sepsis care. In addition, testing and iterative optimization of the accuracy of the Code Sepsis activation may employ direct observation of care for a convenience sample of patients during ED triage and comparison of activation criteria to clinician judgment, final sepsis diagnosis based on chart review, and electronic sepsis queries. Finally, pilot testing of the draft protocol may be conducted on a small convenience sample of patients (<20) identified by ED clinicians as having possible sepsis. We will collect anonymous data about completion of Code Sepsis processes during pilot testing.

Phase #1: Pre intervention (1 year)

- Control EDs: Standard care
- Intervention ED: Standard care.

Phase #2: Intervention roll-in

- Control EDs: Standard care
- Intervention ED: Launch and fine-tuning of Code Sepsis protocol, fine tuning of Code Sepsis activation mechanism.

Phase #3: Full intervention

- Control EDs: Standard care
- Intervention ED: Full implementation of Code Sepsis protocol

Phase #4 (operational): Continuation of the Code Sepsis protocol (with or without revision) by the intervention ED and/or adoption elsewhere within the Intermountain Healthcare system is expected to be contingent on observed effects of protocol implementation. It is possible that an inadequate benefit/risk ratio could lead to a decision not to continue the Code Sepsis protocol.

#### 5.1 Standard Care

Patients arriving to the control EDs (all study phases) and the intervention ED during study Phase #1 will receive care as per then-current ED practices and protocols, guided by clinician judgment within a system-wide care process model for sepsis. As of early 2019, ED standard care for sepsis applicable at all study sites includes a standardized Care Process Model, expected completion of a standardized checklist, and standardized order sets.

#### 5.2 Code Sepsis Protocol

The Code Sepsis protocol (Figure 3) has six steps developed in collaboration with ED-based study team members and ED leaders (including physicians, nurses, pharmacists, and others) from the implementation ED and the Intermountain system. The current draft protocol was further iteratively revised based on input derived from the proposed multidisciplinary team during *in situ* high-fidelity simulation and during informal/ad hoc operationally-oriented pilot testing of steps 1-5 during live patient care. The below protocol will be adapted further prior to and after implementation to ensure the protocol is feasible, efficient, and functions as intended based on stakeholder input and, as needed, additional protocol element testing during simulation and/or live patient care. Further revision will occur, during the protocol run-in phase and as needed based on observed findings and stakeholder input.

Figure 3. Current Code Sepsis protocol based on iterative revision using simulation testing, stakeholder input, & live pilot testing.

- Identify likely sepsis patient from prehospital notification call data (nurse), at ED triage (nurse/physician), or on ED room placement (nurse or physician), adapting local and national practice for stroke team activation.
- 2) Mobilize ED personnel and equipment to meet patients on arrival to the ED room using methods and communication networks already developed for ED trauma and stroke teams.
- 3) Concurrent patient evaluation and data collection by multiple disciplines (20-25 minutes), to include bedside assessment (e.g. history, examination, vital signs, allergy and medication history) by the physician, nurse and pharmacist; IV placement; blood and urine sampling; point-of-care laboratory testing, including lactate and urinalysis; and portable X-ray imaging. Appropriate therapeutic interventions will continue in parallel during the nominal data collection phase.
- 4) Team "huddles" to decide if sepsis diagnosis has been confirmed, disproven, or remains indeterminate. The physician may complete this step by announcing clinical decision-making to the team at any time. The nurse will request a decision huddle at 25 minutes into the Code Sepsis event if it has not previously been performed.

- 5) Proceed with next therapeutic and/or diagnostic steps including, for confirmed sepsis patients, immediate initiation of an appropriate antibiotic regimen chosen from a range of options contained in a Code Sepsis antibiotic pack brought to the bedside by a pharmacist on protocol activation. Code Sepsis antibiotic regimens have been selected based on published guidelines and local antibiotic resistance patterns with input from ED clinicians, pharmacists, and infectious disease/antibiotic stewardship personnel.
- 6) If initial huddle pronounced sepsis status as "indeterminate," return to step #4 after additional 20-25 minutes to follow up on additional diagnostic results (e.g. urinalysis, complete blood count
- 7) For antibiotic-treated patients, follow-up by antibiotic stewardship pharmacist active de-escalation or cessation as appropriate.

Additional protocol elements/details:

- Code Sepsis team members:
  - ED attending physician +/- ED resident physician or medical student
  - ED triage nurse
  - ED unit coordinator (i.e. unit secretary)
  - o ED nurses x2
  - o ED patient care technician
  - ED phlebotomist x1-2
  - ED pharmacist as available
  - o ED X-ray technician
- Code Sepsis electronic order entry: Code Sepsis order sets for diagnostic evaluation and antibiotic treatment will be constructed and activated at the intervention ED's electronic medical record with the beginning of study Phase #2. Order sets will help speed up diagnostic testing and treatment initiation, aid care standardization, and facilitate Code Sepsis event tracking and data collection.
- Code Sepsis clinical team training: With active support from intervention hospital clinical leadership as well as Intermountain's system-wide ED leadership team, the Code Sepsis ED Implementation Team will provide clinical staff in the implementation ED with training on the Code Sepsis protocol during the months prior to study Phase #2. Primary training will include distribution of instructional materials, direct education at clinical staff meetings, targeted in-person education, and *in situ* simulation. Primary training will complete early in study Phase #2, with consolidation training, protocol reminders, physician detailing, and targeted clinician reeducation continuing through study Phase #3.

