#### 3.5 Study Overview

To assess feasibility and test the preliminary efficacy of ED-based Code Sepsis teams activated on or before patients' ED arrival, we will pursue a Phase 2a implementation trial involving Code Sepsis team activation in one ED (Intermountain Medical Center [IMC]) while collecting contemporaneous control data at two other urban EDs (Utah Valley Hospital and Dixie Regional Medical Center [control sites], Table 1).

Months 1-12: Collect baseline data (all sites), refine Code Sepsis protocol, and train ED staff at IMC.

Portions of baseline data may be collected in a retrospective fashion. At the intervention site during this period, we may also undertake preparatory work to Code Sepsis protocol launch, including anonymous patient care observations to evaluate care processes; pilot testing of the draft Code Sepsis protocol or its components; and testing of the

Figure 1. Code Sepsis implementation and data collection for Aim III.

accuracy of Code Sepsis activation mechanisms.

• Months 13-15: Run-in period: implement Code Sepsis protocol at IMC, optimize protocol & its trigger.

 Months 25-36: Continue Code Sepsis protocol at site A (intervention ED). Continue standard care processes for sepsis without change (control condition) at two non-intervention EDs Using contemporaneous controls and rigorous statistical methods, we will assess how implementation of the Code Sepsis protocol affects process and patient outcomes in the intervention ED (Figure 1). Continuation of the Code Sepsis protocol (with or without revision) by the intervention ED and/or adoption elsewhere within the Intermountain Healthcare system is expected to be contingent on the results of these analyses.

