## 9. HUMAN SUBJECTS

We will prospectively assess the effect of a system-level intervention on the organization of ED sepsis care using an augmented pre-/post-intervention design. In the post-intervention period, the studied intervention — early activation of ED teams for patients likely to have sepsis — will be adopted as standard care at Intermountain Medical Center. As such, no patients arriving to any ED during the pre-intervention or to a non-intervention control ED will be exposed to the intervention. Conversely, all patients arriving to the Intermountain Medical Center ED in the post-intervention phase will be exposed to the intervention.

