#### Study phases and associated exposures

Dhaca	Detient CD envivel deter	Care received by patients		
Phase	Patient ED arrival dates		Intervention EDs	
Pre-intervention analysis	11/13/2018-11/12/2019	Standard care	Standard care	
Post-intervention wash-in	11/13/2019-2/12/2020	Standard care	Code Sepsis protocol	
Post-intervention analysis	2/13/2020-2/12/2021	Standard care	Code Sepsis protocol	

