### Data analysis

Analyses for causal inference regarding primary, secondary and safety outcomes will employ a quasi-experimental method called *difference-in-difference* (DID) analysis to control for secular trends and confounding of unknown individual factors associated with the outcome of interest. The DID approach will provide an estimate of the effect of the Code Sepsis intervention on primary, secondary, and safety outcomes by comparing the intervention and control hospitals during the pre- and post-implementation periods (Figure 1).

For the primary outcome, DID analysis will use multivariable linear regression to compare the adjusted mean door-to-

antibiotic time (primary outcome) at the intervention hospital

pre- versus post-implementation of the Code Sepsis protocol using the measured change at contemporaneous control non-intervention hospitals to control for pre-/post-intervention changes not attributable to protocol implementation after adjustment for potential confounders.

The following equation will be used to estimate the adjusted mean differential change in the primary outcome, door to antibiotic time:

$$Y_{igt} = \beta_0 + \beta_1 Int_g + \beta_2 Post_t + \beta_3 (Int_g * Post_t) + \beta_4 Cov$$

Where  $Y_{igt}$  is the door-to-antibiotic time for patient *i* treated at an intervention or non-intervention ED *g* at pre- or post-intervention time *t*. *Int* is a binary indicator for the subject being treated at an intervention hospital; *Post* is a binary indicator the post-intervention period; and *Cov* represents a vector of patient-level covariates. The  $\beta_3$  parameter from the regression model presented above estimates the adjusted mean differential change in door-to-antibiotic time observed in the Code Sepsis intervention hospital compared to the control hospital. We will consider the Code Sepsis intervention to have had an impact if  $\beta_3$  is statistically significant and different from zero.

The parallel trend assumption will be tested using the approach outlined by Callaway and Sant'Anna. This approach allows for testing the parallel trend assumption after conditioning on covariates. This approach is

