limited in that it only considers the control and treated groups during the pre-implementation phase. If the pre-test of parallel trends assumption fails, then we will weight the gamma regression model with propensity scores. As demonstrated by Stuart *et. al*, this will balance the covariates amongst the four study groups defined by their treatment status as well as time (pre vs post). We will leverage the covariate balancing propensity score (CBPS) library in R to generate propensity scores. This weighting approach can recover treatment effects in that it allows for adjustments due to observed baseline covariates that differ either across groups or over time. Covariates that will be used in generating propensity scores will include age; sex; weighted Elixhauser comorbidity score; English language preference; first-available heart rate, temperature, systolic blood pressure, and respiratory rate; acute physiology score; ED arrival at nightime (10 pm to 6:59 am), ED arrival on weekend (midnight Saturday to 11:59 pm Sunday), SARS-CoV-2 test result (positive, negative, or not performed during ED-associated hospitalization or within 14 days preceding ED arrival); and insurance type. For analyses involving a cohort of patients with sepsis, propensity score covariates will additionally include arrival to ED via ambulance; presentation from a long term care facility; serum lactic acid level checked and ≥2 mmol/dL; ED SOFA score; and ED-diagnosed infection source.

In order to account for the right skew known to exist in door-to-antibiotic time we will use generalized linear gamma regression to estimate the DID. Evaluation of secondary outcomes will employ an analogous approach using multivariable linear, Poisson, logistic, or gamma regression as appropriate. Data from the wash-in phase will be excluded from DID analyses. All multivariable models will be adjusted for demographic and clinical parameters with known or plausible associations with both outcomes and treatment hospital, presentation before or after Code Sepsis implementation, and/or Code Sepsis activation as well as select precision variables as detailed below. Analyses for secondary, safety, and heterogeneity of treatment effect outcomes will not be adjusted for multiple comparisons and will therefore be considered hypothesis generating.

Statistical significance will be set to p < 0.05. All analyses will be conducted with R.

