#### Sensitivity analyses

*Key sensitivity analysis*: To augment causal inference from the primary analysis and evaluate for the possibility of non-parallel trends in the primary outcome at intervention versus control hospitals during the preintervention phase, we will perform a sensitivity analysis evaluating the adjusted primary outcome (door-toantibiotic time) with a multi-group interrupted time series analysis. The following segmented regression suggested by Ryan et.al. will be used to estimate the effect of the Code Sepsis intervention on door-toantibiotic time:

$$Y_{igt} = \beta_0 + \beta_1 Time + \beta_2 (Time * Int_g) + \beta_3 Post_t + \beta_4 (Int_g * Post_t) + \beta_5 Cov$$

Where  $Y_{igt}$  is the door-to-antibiotic time for patient *i* treated at an intervention or non-intervention ED *g* at pre- or post-intervention time *t*. *Time* is a continuous variable indicating the bi-weekly count from the start of the observation period; *Int* is a binary indicator for the subject being treated at an intervention hospital; *Post* is a binary indicator for the post intervention period. The  $\beta_4$  parameter from the regression model is interpreted in nearly the same manner as the primary outcome, in that it estimates the adjusted differential change in door-to-antibiotic time between the control and CodeSepsis hospitals. This model allows for the trends to differ between the intervention and control hospitals during the pre-intervention phase. We will consider the Code Sepsis intervention of have had an impact if  $\beta_4$  is statistically significant and different from zero.

In order to account for the right skew known to exist in door-to-antibiotic time we will use generalized linear gamma regression to estimate the DID. Data from the wash-in phase will be excluded from the sensitivity analysis.

- Other primary outcome sensitivity analyses:
  - Repeat primary analysis among patients in "sepsis high-risk" cohort who received antibiotics in the ED.
  - Repeat primary analysis in the dataset comprising all *encounters* (≥1 encounter per patient) meeting sepsis criteria between ED arrival and ED departure, using generalized linear models with a random effect for patient to account for non-independence.
  - $\circ$   $\,$  Missing data sensitivity analyses as described in the "Missing Data" section  $\,$

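### Staff training at the intervention ED falls inside the baseline year analysed as unexposed; if it speeds sepsis care, the DID is biased toward no effect, and late training would attenuate the time-series check more

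*Protocol*

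**What the plan says.** Protocol Section 4.2.5 dates phase #1 from 13 November 2018 to 12 November 2019 and starts phase #2 on 13 November 2019, with no gap.

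Several activities at the intervention ED are placed in or just before that boundary:

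- Section 5.2: clinical staff receive "training on the Code Sepsis protocol during the months prior to study Phase #2", by written materials, staff meetings, in-person teaching and in situ simulation. Primary training finishes early in phase #2. The Code Sepsis order sets go live only when phase #2 begins.
- Section 3.5: the tasks for months 1 to 12, alongside baseline data collection, are to "refine Code Sepsis protocol, and train ED staff at IMC".
- Section 5: a development phase (Phase #0) overlaps phase #1, and "pilot testing of the draft protocol may be conducted on a small convenience sample of patients (<20", that is, fewer than 20.

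Against this, Protocol Section 9 says that "no patients arriving to any ED during the pre-intervention or to a non-intervention control ED will be exposed to the intervention". The SAP table of study phases carries the same 12 months as "Pre-intervention analysis", with standard care at every site. The SAP removes only the wash-in months from the DID and from the interrupted time series. Of the latter it says: "This model allows for the trends to differ between the intervention and control hospitals during the pre-intervention phase". No listed sensitivity analysis leaves out the pre-launch months or any pilot encounters.

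**The concern.** The DID takes the phase #1 mean at the intervention ED as the outcome without the programme. Teaching that ED's clinicians rapid sepsis recognition before launch could shorten door-to-antibiotic time there and not at the control EDs. Part of the programme's effect would then sit in the baseline and be subtracted from the estimate.

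The planned safeguards do not cover this. The parallel-trends pre-test looks only at the pre-implementation phase, so a late dip at one ED could make it fail. The fallback then weights on observed covariates, and staff training is not one of them. The key time-series analysis fits one linear slope per group through both periods. It would read a late-baseline dip as a trend already under way, project it forward and deduct it. The primary and key sensitivity analyses could then disagree because of when training was scheduled. Protocol Sections 3.5 and 5 make continuation or wider adoption depend on the observed effects, so the size of the estimate matters.

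**Working it through.** **Inputs.** From Protocol Section 7.3 and SAP Power: 1,650 intervention-ED and 2,200 control-ED sepsis patients a year; mean 170 minutes, SD 75; 50 minutes under Code Sepsis; 30% activation; 16-minute detectable difference at 90% power. From SAP Data analysis: "Statistical significance will be set to p < 0.05", and an effect is claimed if the coefficient is "statistically significant and different from zero", read here as two-sided. **Assumed:** the size, shape and duration of any training effect.

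**The plan's own figure.** In closed form, the DID SE is 75 × √(2/1,650 + 2/2,200) = 3.45 minutes. The 90%-power difference is (1.960 + 1.282) × 3.45 = 11.2 minutes, and power at 16 minutes is 99.6%. The stated 90% is not reproduced; it would need an SE of 16/3.242 = 4.94. The simulation details are not given, so this does not show the figure to be wrong, and this point does not rest on it. Both SEs are used below.

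**Expected effect.** Section 7.3 implies an average of 0.30 × (170 − 50) = 36 minutes. The 16 minutes is the smallest effect for which 90% power is claimed.

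**Pilots.** At most 19 × 120/1,650 = 1.4 minutes off the baseline mean, if all 19 enter the sepsis cohort and gain the full 120 minutes.

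**Training, DID.** Bias = step × months/12. For a 16-minute effect:

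- 3-minute step, 3 months: 16 − 3 × 3/12 = 15.25
- 10-minute step, 3 months: 16 − 10 × 3/12 = 13.5
- 10-minute step, 6 months: 16 − 10 × 6/12 = 11.0

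At 13.5 minutes, power is Φ(13.5/3.45 − 1.96) ≈ 97%, or Φ(13.5/4.94 − 1.96) ≈ 78% with the SE implied by the plan.

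**Training, both models.** Noise-free weighted least squares on 26 two-week bins per phase, wash-in removed, no covariates, minutes scale. The time-series model has Time, Time × Int, Post and Int × Post, plus a site main effect. Three months is 6.5 bins, so ranges cover 6 and 7 bins.

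| Assumed change at the intervention ED in phase #1 | True effect | DID | Time series |
|---|---|---|---|
| 3-minute step, last 3 months | 16 | 15.2–15.3 | 13.0–13.3 |
| Ramp to 10 minutes, last 3 months | 16 | 14.8 | 10.9 |
| 10-minute step, last 3 months | 16 | 13.3–13.7 | 5.9–7.0 |
| 10-minute step, last 6 months | 16 | 11.0 | 1.6 |
| 10-minute step, last 3 months | 36 | 33.3–33.7 | 25.9–27.0 |
| 10 minutes, evenly over the year | 16 | 6.0 | 6.0 |
| 10 minutes, first 3 months only | 16 | 13.3–13.7 | 20.4–20.7 |

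The SAP prints the time-series equation without a site main effect. Fitted that way, the late-step rows change little (7.4 with the step over 6 bins, 0.2 for six months). The last two rows do depend on the main effect: without it, evenly spread contamination lowers the time series more than the DID, and the early case is no longer inflated.

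**The case against.** The strongest reply is that no harm is shown. Neither document says that training alone changes door-to-antibiotic time. What is tested is team activation with an antibiotic pack brought to the bedside, and the order sets start only with phase #2. A 10-minute training effect is 63% of a 16-minute effect (10/16), before the programme is running. Against the 36 minutes implied by Section 7.3, the same three-month step costs the DID about 2.5 minutes. All of this stands, and it limits the point to a conditional one.

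Four stronger readings are tempting, and the documents do not support them:

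- *The baseline is contaminated.* The timing is documented; a training effect is not.
- *Live pilots happen in phase #1.* They only may happen, the overlap is not dated, and Section 5.2 describes some simulation and ad hoc piloting as already done.
- *The time series always suffers more.* That needs a late change. Section 5.2 suggests late training, but Section 3.5 allows months 1 to 12. Evenly spread contamination hits both models equally, and early contamination can make the time-series estimate too large (both with the site main effect included).
- *Pilot encounters cannot be removed because pilot data are anonymous.* Section 5 makes the process-completion data anonymous. Section 6.5 separately lists encounter ID and Code Sepsis activation, with no restriction to phase #3, and Section 6.1 allows chart review.

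The reply does not answer three things: the months are analysed as clean, no planned analysis tests that assumption, and Sections 5 and 9 conflict on exposure.

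**Conclusion.** The point holds as a conditional risk. Training and simulation at the intervention ED, and possibly a few pilots, sit inside a baseline year that is analysed in full as unexposed. If training speeds care, the DID is biased toward no effect. If the change comes late in phase #1, the time-series check is attenuated by roughly three to four times as much as the DID: in the three-month, 10-minute case about 9 to 10 minutes are lost, against about 2.3 to 2.7.

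The size is unknown, and every training figure above rests on an assumed effect. With late contamination, what is at risk is the effect size, power and agreement between the two analyses, not false-positive control. Pilots are a minor part. This merits a prespecified sensitivity analysis and a text correction; it does not call for a different primary analysis.

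**What to change.** 1. Prespecify a sensitivity analysis of both the DID and the time-series model that drops the last three months of phase #1 at all three EDs and, separately, the last six. Drop the same calendar months of phase #3 to keep seasons balanced (13 August to 12 November 2020; 13 May to 12 November 2020). A cut at the recorded start of the main staff-training programme could replace the fixed windows. Do not cut at the first training, simulation or pilot of any kind: Sections 3.5 and 5.2 allow that date to fall at or before the start of phase #1, which could leave no baseline.
2. Flag any pilot-activation encounters with the encounter ID and activation fields in Protocol Section 6.5, and exclude them from phase #1.
3. Reconcile the Section 9 statement on exposure with Phase #0 in Section 5.

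**Cost.** SAP wording and two re-runs of each model. The DID SE in the sensitivity run rises from 3.45 to 3.45/√0.75 ≈ 3.99 minutes with three months dropped from each phase, and to 3.45/√0.5 ≈ 4.9 with six. The time series loses more: on the same grid with SD 75 and the site main effect, its SE goes from about 8.2 to about 10.3 minutes with three months dropped and 13.4 with six. The primary analysis loses at most 19 patients.
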